7.1.3 Precautions

SB-913 is an investigational product, and there is a potential risk of severe hypersensitivity reaction (e.g., anaphylaxis). Emergency medical equipment must be available during the infusion in case the subject has an allergic response, severe hypotensive crisis, or any other reaction to the infusion. Vital signs (temperature, heart rate, respiratory rate, and blood pressure) must be taken before, during, and after infusion (see Appendix 1 and refer to the Study Reference Manual). In the unlikely event that the subject develops sepsis or systemic bacteremia following SB-913 infusion, appropriate cultures and medical management should be initiated.

All dangerous goods materials, including diagnostic specimens and infectious substances, must be transported according to the instructions detailed in the International Air Transport Association (IATA) Dangerous Goods Regulations.

7.1.4 Dose Modifications

No dose modifications are possible within an individual subject since this is a single infusion study.

7.2 Concomitant Medication and Supportive Care

The Principal Investigator will record all concomitant medications, including over-the-counter medicinal products, dietary supplements, herbal medications, and medications given in treatment of AEs, taken by a subject from Screening throughout the course of the study on the concomitant medications page in the subject's case report form (CRF).

Subjects who received ERT prior to study enrollment should continue to receive ERT during the study as per standard of care unless they undergo ERT withdrawal (see Section 11.4), except during the week of the SB-913 infusion, and such treatment should be recorded on the concomitant medications page.

Treatment with prednisone or equivalent corticosteroid and pre-treatment with acetaminophen (Tylenol or Paracetamol) and diphenhydramine hydrochloride or equivalent medication should also be recorded on the concomitant medications page.

In the proposed study, subjects will be screened for neutralizing antibodies to AAV2/6. Subjects that test positive to neutralizing antibodies to AAV2/6 will not be enrolled in this study. Cell-mediated immunity to the viral capsid may be attenuated/abrogated with a course of immunosuppression since the viral capsid is not encoded in the vector. Therefore, in this study, subjects will receive pretreatment with oral prednisone or equivalent corticosteroid starting 2 days prior to SB-913 infusion and as described in Appendix 3. If any subject develops increased aminotransferases in spite of the prednisone or equivalent corticosteroid treatment, the prednisone or equivalent corticosteroid regimen may be adjusted or restarted after consultation with the Medical Monitor.

8.1.1 Potential On-Target Effect on Albumin

Albumin is the most abundant plasma protein, accounting for 55-60% of plasma proteins. The total body albumin pool is about 250 to 300 g for a healthy 70 kg adult, with approximately 42% of this in the plasma compartment and the remainder in the extravascular space. The latter is recirculated into the vascular compartment via the lymphatics. Albumin synthesis in humans occurs only in the liver. The rate of albumin synthesis in a healthy adult is 12-25 g/day, but varies depending on the nutritional and health status of an individual. The capacity to increase albumin synthesis is limited (2-2.7x normal) since much of the liver synthetic machinery is already devoted to albumin synthesis at rest. Daily albumin degradation is approximately 14 g/d or ~5% of total body protein turnover. Albumin is broken down in most organs of the body, with 40-60% being degraded by muscle and skin, ~15% by the liver, and ~10% each by kidney and gastrointestinal tract.

The function of albumin is well established and includes maintenance of plasma oncotic pressure, acid-base balance, antioxidant function, and anticoagulant effects. It also binds to numerous compounds, such as hydrophobic organic anions, long chain fatty acids, bilirubin, hematin, and hormones such as thyroxine. Despite the importance of albumin, approximately 30 individuals with analbuminemia have been described, in which mutations in the albumin gene result in mRNA splicing errors and premature stop codons (Watkins et al. 1994). These subjects do have some circulating albumin (<1 g/L), possibly due to gene leakage. The subjects' bodies appear to compensate by slowing the rate of albumin degradation. Surprisingly, these subjects have minimal pathology, limited to peripheral edema, lipodystrophy (lower limb obesity), fatigue, and hyperlipidemia (Minchiotti, et al. 2013; Prinsen & van der Velden 2004; Nicholson et al. 2000). The hemodynamic effects of analbuminemia are minor, consisting of a minor reduction in oncotic pressure (16 vs 25 mm Hg) and arterial pressure leading to increased renin and aldosterone secretion.

Given the rate of albumin production by the liver (12-25 g/day), it can be estimated that the conversion by SB-913 of as little as 0.01% of albumin alleles to hIDS synthesis would yield potentially therapeutically beneficial IDS levels (>1% of normal) in plasma (Muenzer et al. 2006; Elaprase FDA summary of approval). The loss of such a small proportion of albumin production is expected to have no adverse consequences. At the individual cell level, the targeted locus is

completely dispensable, since albumin has no autocrine role. At the organism level, heterozygous disruption of albumin yields no symptoms, and even homozygous disruption is tolerated as described above. Therefore, disrupting < 1% of the albumin alleles is predicted to have no adverse phenotype. Moreover, given the intronic location of the ZFN target site, ZFN cleavage and subsequent DNA repair in the absence of hIDS integration (e.g., small insertion and deletion mutations at the site of ZFN cleavage) will be functionally inert with respect to albumin expression. A recent review of the genetic targeting of the albumin locus to treat hemophilia in murine models highlights the usefulness of targeting a highly active heterologous gene like albumin; neither transaminitis nor perturbations in serum albumin levels were observed, and few off-target integration sites were detected (Davidoff & Nathwani 2016).

8.1.2 Potential Off-Target Effects

An unbiased integration site assay was established to identify ZFN cleavage sites and subsequent insertion of a donor oligonucleotide duplex in the genome (based on Gabriel et al. 2011). This assay allows for evaluation of all potential integration sites within the genome. The integration site assay was run using the SB-913 ZFNs (SB-47171 and SB-47898), and yielded a ranked list of 39 candidate cleavage sites. As expected, the top ranked locus in the human genome was the intended target site within albumin intron 1. A follow-up indel analysis performed in human primary hepatocytes transduced with rAAV2/6 encoding the SB-913 ZFNs revealed significant modification only at the on-target site in albumin intron 1 (6.1% for low dose and 33.5% for high dose) but at no other candidate cleavage site.

For the SB-FIX program (BB-IND 16721), which uses ZFNs highly similar to the SB-913 ZFNs, the integration site assay revealed a single, low activity off-target site. Due to the similarity of the ZFN reagents, this off-target site was also considered for further analysis in the SB-913 program. The off-target site was mapped to exon 38 (out of 48 exons) of the SMCHD1 gene. SMCHD1 has been linked to chromosome X-inactivation, tumor suppression, DNA damage repair, and facioscapulohumeral muscular dystrophy (FSHD) type 2.

A mouse knockout (by genetrap/gt) of the murine homolog of SMCHD1 has been generated (Blewitt et al. 2008). Although male knockout mice (Smchd1 gt/gt) develop normally, female knockout mice exhibit embryonic lethality due to problems with X chromosome inactivation and misregulation of CpG methylation. This indicates a role for SMCHD1 in embryogenesis in the female mouse, and suggests that only the loss of both SMCHD1 copies in female patients could potentially pose a problem. Furthermore, it is unclear whether X-inactivation would have any impact on liver hepatocytes, which are often polyploid. Male knockout mice show normal embryonic development but increased lethality after birth (Leong et al. 2013); surviving mice appear normal and show no predisposition or susceptibility to tumor formation. When the male knockout mice were crossed into a premalignant Eu-Myc transgenic mouse model, some hematopoietic cancers were detected in homozygotes (Leong et al. 2013).

It has been suggested that SMCHD1 is recruited to the site of DNA damage and that its depletion could alter DNA damage response signaling and cell survival (Tang et al. 2014). However, no evidence for decreased cell survival or spontaneous activation of apoptosis (cleaved Parp1) or DNA damage markers (Kap-1 phosphorylation) was seen during *in vitro* dose titration studies with up to 45% SB-913 ZFN on-target activity.

SMCHD1 mutations have been associated with FSHD type 2, which is an autosomal dominant muscular dystrophy affecting facial, shoulder girdle, upper arm, and other muscle tissues

(Larsen et al. 2015). FSHD type 1 is linked to the contraction of macrosatellite D4Z4 repeats and misregulation of the DUX4 transcript in myoblasts (Statland & Tawil 2014). The far less common FSHD type 2 (about 5% of all cases) has been linked to mutations in SMCHD1 (Lemmers et al. 2012). However, SB-913 ZFN expression should be restricted to hepatocytes due to the use of the liver-specific ApoE/hAAT promotor, and no liver-related symptoms have been reported with FSHD. Moreover, *in vivo* studies with the surrogate mouse SB-913 ZFNs revealed no significant modification of the albumin locus in tissues other than liver tissue, confirming the ZFN's tissue-specific expression.

Dose titration studies carried out *in vitro* in human hepatocytes with SB-913 ZFNs showed that the SMCHD1 off-target site was modified only at low levels, nearly 100-fold below those observed at the albumin intron 1 on-target site, and modification levels were generally within the range seen in mock-treated cells or control samples. Only at higher doses of AAV2/6 SB-913 ZFNs, which corresponded to an on-target activity of more than 20%, were the levels of off-target modification at SMCHD1 consistently above background. *In vitro* studies established that non-human primate albumin ZFN surrogate reagents cut the conserved SMCHD1 off-target in similar fashion with about 100-fold less efficiency than at the albumin on-target locus. Accordingly, analysis of non-human primate *in vivo* samples with on-target ZFN activity of up to 2.1% found no significant off-target activity behavior in cultured cells is predictive of the *in vivo* situation in non-human primates and potentially humans.

8.1.3 Carcinogenicity

There is a risk that people who receive gene transfer may develop tumors derived from their genetically modified cells. This risk has been seen with viral gene transfer vectors that integrate randomly into the cellular DNA where they may affect genes controlling cell proliferation. The rAAV2/6 vector donor will integrate specifically in the albumin ZFN DSB site. In toxicity studies, no tumors were identified. For evaluation of liver carcinogenicity the current study adopts the hepato-cellular carcinoma (HCC) screening recommendation for high risk subjects (e.g., chronic hepatitis C or B), which includes monitoring AFP and liver MRI. Liver biopsy will be performed if there is an abnormal AFP and a >2 cm mass in the liver (El-Serag & Davila 2011).

8.2 **Prednisone (or Equivalent Corticosteroid)**

Prednisone is a glucocorticoid. Glucocorticoids are adrenocortical steroids, both naturally occurring and synthetic, which are readily absorbed from the gastrointestinal tract.

The following adverse reactions have been associated with the use of glucocorticoids:

- Thinning of bones (osteoporosis), which may lead to fractures or compressions, especially true of vertebral bodies (backbone).
- Loss of blood supply to bones (aseptic necrosis), which may cause severe bone pain, fractures (especially of the hip and shoulder), and which may require surgical correction.
- High blood pressure (hypertension).
- Increased pressure in the eye (glaucoma).
- Permanent clouding of vision in one or both eyes (cataracts).
- Weight gain with increased appetite and fluid retention.

- Facial fullness.
- Increase in body hair and acne, and tendency to easy bruising and thinning of the skin.
- Increased risk of infections while on high dose continuous steroid therapy.
- Interference with growth.
- Muscle cramps and joint pain.
- Changes in the menstrual cycle.
- Elevations in blood sugar (diabetes).
- Suppression of adrenal glands' ability to make necessary cortisone at times of stress (adrenal insufficiency).
- Irritation of stomach and esophagus with possible ulcer type symptoms and, rarely, bleeding.
- Emotional disturbances.

Dietary guidelines will be provided to subjects while on prednisone or equivalent corticosteroid to help alleviate some of the side effects including blood sugar elevation, associated with the use of glucocorticoids (refer to the Study Reference Manual).

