9.28 Liver Biopsy

The proposed mechanism of action of SB-913 is to introduce the hIDS transgene into a precise location in the albumin locus. To determine the efficiency of SB-913, liver tissue will be obtained by liver biopsy, unless contraindicated by the Principal Investigator or physician, and analyzed by histopathologic examination, testing for GAG levels, and high-throughput sequencing of the albumin locus. Further, subjects with an elevated AFP or MRI mass suspicious for HCC or greater than 2 cm will undergo liver biopsy. Histopathologic examination and genomic analysis will be performed to determine the origin and nature of the tumor. For details, see Appendix 4 and refer to the Study Reference Manual.

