11.5 Study Stopping Rules

The safety data for all subjects within a cohort will be evaluated by the SMC at least 4 weeks after the last subject within that cohort was infused with SB-913. Safety data including AEs and clinical laboratory results (chemistry, hematology, etc.) will be evaluated to determine if it is safe to dose escalate. Subjects in the subsequent cohort may be screened and enrolled prior to the safety review

but will not be infused until the SMC has reviewed the data and approved the study for cohort escalation.

The SMC will also be convened to recommend whether the study should be stopped if any of the following criteria are met:

- Any one Grade 3 or higher AE, or any two Grade 2 AEs in the same system organ class that last more than 2 weeks with therapy, provided these AEs are not related to the primary MPS II disease or treatment of the MPS II disease.
- SAE not related to the primary MPS II disease.
- Death of a subject.
- Development of a malignancy.

The study may also be stopped for any of the following reasons:

- Sangamo, in consultation with the SMC or Regulatory Agency, decides for any reason that subject safety may be compromised by continuing the study.
- Sangamo decides to discontinue development of SB-913.

If stopping criteria are met, no further dosing of subjects will be performed until a substantial amendment is submitted to the regulatory authority(ies) for review, and the amendment has been approved by the site IRB/IEC or equivalent. When no further enrolling or dosing decisions are required of the SMC, the SMC will no longer meet. Sangamo will review subject safety data on an ongoing basis.

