13.1 Determination of Sample Size

This study will enroll up to 32 subjects (2 subjects in each of 8 cohorts, with potential enrollment of approximately 2 additional subjects in any cohort). The sample size for this study was not based on statistical considerations, but is considered sufficient to provide preliminary assessments of the safety and tolerability of SB-913 in subjects with MPS II, as well as biochemical changes related to the pathophysiology of MPS II. Subjects who prematurely discontinue the study prior to the 12 months of study follow-up (i.e., subjects who were enrolled but not dosed, were lost to follow-up, or discontinued prematurely for another reason) may be replaced at the discretion of Sangamo.

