13.4 Primary Endpoint

The primary endpoint of this study is the incidence of treatment-emergent AEs (including SAEs).

Additional safety evaluations will include:

- Routine hematology, chemistry, and liver function laboratory tests, vital signs, physical exam, ECG, ECHO, and concomitant medications.
- Cranial nerve exam and muscle strength testing.
- Serial AFP testing and MRI of liver to evaluate for liver mass.

Safety assessment will be performed on all subjects. All reported AEs will be coded to a standard set of terms using the Medical Dictionary for Regulatory Activities (MedDRA).

Treatment-emergent adverse events will be summarized overall and by treatment cohort. For each subject, the maximum reported severity of each adverse event will be used in the summaries by

severity grade. In addition, all serious adverse events and AEs related to study treatment will be summarized.

Laboratory data will be summarized for each time-point at which specimens are collected. Change-from-Baseline values may be calculated for selected laboratory parameters. Shift-tables (Change-from-Baseline relative to the normal range) may be constructed for selected laboratory parameters.

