APPENDIX 4: INSTRUCTION FOR LIVER BIOPSY SAMPLE COLLECTION AND TISSUE PREPARATION

SB-913 uses ZFN-gene specific targeted insertion of a hIDS donor transgene into the liver albumin genome locus in subjects with MPS II to provide long-term production of hIDS. To determine the efficiency of SB-913, liver tissue will be obtained by liver biopsy for analysis by histopathologic examination, testing for GAG levels, and site specific molecular analysis at the albumin locus. AFP levels will be monitored throughout the study, and abnormal results will be investigated by clinical evaluation and MRI. Any subject who has an elevated AFP and/or an MRI mass suspicious for HCC or greater than 2 cm will undergo liver biopsy. Histopathologic examination and integration site analysis will be performed to determine the origin and nature of the tumor.

Liver Biopsy Sample Collection and Tissue Preparation

Liver biopsy will be obtained at selected visits unless contraindicated by a Principal Investigator or physician. The liver biopsy should be divided into 3 samples when possible. One liver biopsy sample will be collected in 10% neutral buffered formalin and processed for histopathological evaluation. Two liver biopsy samples will be flash frozen in liquid nitrogen. Samples may be stored in a -80°C freezer before shipment. The weight of liver tissue obtained from each biopsy sample will be forwarded to Sangamo.

The efficiency of SB-913 in targeting insertion of hIDS donor transgene to the liver will be measured by site specific molecular analysis of integration events at the albumin locus.

Additionally, the frequency of other genomic modification events like small insertions and deletions (indels) will be determined by Next Generation Sequencing (NGS) at the albumin locus and at the SMCHD1 locus, the only known off-target site of SB-913.

In addition, for any subject who undergoes liver biopsy due to an elevated AFP and/or an MRI mass suspicious for HCC, the albumin locus will be sequenced by NGS to examine the genetic diversity at the albumin ZFN cleavage site, which may provide information about the clonal origin of the suspicious mass. A single or limited number of modified albumin genotypes or AAV integration sites would indicate that the cells were derived from the clonal expansion of modified hepatocytes. A similar sequencing analysis will also be performed on the SMCHD1 locus to evaluate the genetic diversity at the only known off-target site of SB-913.

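### The protocol states the trigger for a for-cause liver biopsy in two ways: raised AFP together with a mass over 2 cm (8.1.3), or either kind of finding alone (9.28 and Appendix 4)

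*Protocol*

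**What the plan says.** Three places in the protocol say when a suspected tumour leads to liver biopsy.

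- Section 8.1.3, Carcinogenicity: "Liver biopsy will be performed if there is an abnormal AFP and a >2 cm mass in the liver". The sentence before it says that this study adopts an HCC screening recommendation for high-risk subjects, based on AFP and liver MRI.
- Section 9.28, Liver Biopsy: "subjects with an elevated AFP or MRI mass suspicious for HCC or greater than 2 cm will undergo liver biopsy".
- Appendix 4: "Any subject who has an elevated AFP and/or an MRI mass suspicious for HCC or greater than 2 cm will undergo liver biopsy". The same paragraph says of AFP that "abnormal results will be investigated by clinical evaluation and MRI". A later paragraph, on sequencing, describes the group again without the size criterion: "for any subject who undergoes liver biopsy due to an elevated AFP and/or an MRI mass suspicious for HCC".

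No section gives an order of precedence. The SAP text available does not mention a for-cause biopsy, so it does not settle the matter.

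Two related provisions depend on tumour findings. Section 13.4 lists among the additional safety evaluations "Serial AFP testing and MRI of liver to evaluate for liver mass". Sections 11.5 and 12.3 convene the Safety Monitoring Committee (SMC) on "Development of a malignancy".

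**The concern.** Section 8.1.3 joins the two findings with *and*. Section 9.28 uses *or* and Appendix 4 uses *and/or*, and both add a mass suspicious for HCC with no size limit. All three are worded as what will happen in this study. A site holding a single abnormal finding therefore gets a different answer depending on the page it opens.

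The product edits the genome of liver cells. Section 8.1.3 itself names the risk of tumours arising from modified cells, and 8.1.2 notes that SMCHD1 has been linked to tumour suppression. Under Appendix 4, the for-cause biopsy supplies the histology and the sequencing at the albumin and SMCHD1 loci from which clonal origin would be judged. Scheduled biopsies fall at Baseline, Week 24 and Week 48 only, while AFP and liver MRI continue at Months 18, 24, 30 and 36. In Years 2 and 3 a for-cause biopsy is therefore the only liver biopsy the protocol provides.

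The ambiguity can work in either direction. A subject may undergo an invasive procedure that the sponsor did not intend, or miss one that it did. The planned cohorts go down to age 5.

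**Working it through.** No power, alpha or event count enters. Section 13.1 states "The sample size for this study was not based on statistical considerations", and the plan gives no figure on this point to reproduce. The check is a truth table.

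**Inputs.** A = AFP raised (treating *abnormal* in 8.1.3 and *elevated* elsewhere as the same, since neither section gives a threshold). L = liver mass larger than 2 cm. S = mass suspicious for HCC on MRI.

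**Rules.**
- Section 8.1.3, read as the operating threshold: biopsy when A and L.
- Section 9.28 and Appendix 4 (*and/or* taken as inclusive): biopsy when A or S or L.

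**Step 1: AFP and size only (2 × 2 = 4 combinations).**

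| A | L | 8.1.3 | 9.28 / App. 4 | Same? |
|---|---|---|---|---|
| yes | yes | biopsy | biopsy | yes |
| yes | no | not stated | biopsy | no |
| no | yes | not stated | biopsy | no |
| no | no | not stated | not stated | yes |

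Section 8.1.3 calls for biopsy in 1 combination and the other two sections in 3. They differ in 3 − 1 = 2 of 4.

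**Step 2: add S (2 × 2 × 2 = 8 combinations).** Section 8.1.3 ignores S, so it calls for biopsy in 2 (A and L, with S present or absent). The other rule calls for biopsy in every combination except the one with no finding: 8 − 1 = 7. Every 8.1.3 case is also a 9.28 case, so they differ in 7 − 2 = 5 of 8:

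1. raised AFP, no large mass, not suspicious;
2. raised AFP with a suspicious mass of 2 cm or less;
3. normal AFP, mass over 2 cm, not suspicious;
4. normal AFP, mass over 2 cm, suspicious;
5. normal AFP with a suspicious mass of 2 cm or less.

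These are counts of logical cases, not expected numbers of subjects. The documents give no rate for any of these findings, so an expected count cannot be computed.

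**Step 3: the weaker reading of 8.1.3.** The section says *if*, not *only if*. Taken strictly, it states one sufficient condition and says nothing about the five cases above. On that reading the sections do not clash logically, but 8.1.3 gives a site no instruction where the other two do.

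**Step 4: other loose ends.** Appendix 4 sends an abnormal AFP to clinical evaluation and MRI and also sends an elevated AFP to biopsy. It does not say whether the first step comes before the second, modifies it or replaces it. Its sequencing paragraph drops the size criterion, so it does not expressly cover a subject biopsied only because a mass exceeds 2 cm.

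**The case against.** The strongest reply is that nothing contradicts. Every subject who meets 8.1.3 also meets 9.28 and Appendix 4, no section forbids a biopsy on one finding, and a site that follows 9.28 complies with all three. Section 8.1.3 sits in the chapter on risks and ends with a literature citation. The procedures are in Section 9 and Appendix 4, which agree in substance. Section 9.28 also refers sites to the Study Reference Manual, which is not available here.

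Much of this stands. A reader might infer that the sections give opposite instructions, but the documents do not support that, because *if* is not *only if*. The triggers differ; they do not oppose one another. It also does not settle the point that 8.1.3 says a biopsy *will* be performed, since the same paragraph uses *will* to describe where the donor integrates.

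What does not stand is the idea that 8.1.3 is mere background. It says what this study adopts for evaluating liver carcinogenicity and then gives the biopsy condition. If either finding alone already required a biopsy, naming both together would serve no purpose, so a site would naturally read the sentence as the threshold. Nothing in the protocol tells the site to prefer 9.28.

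**Conclusion.** The inconsistency is real and is wrong as written. With 8.1.3 read as the operating threshold, the triggers differ in 2 of 4 AFP-by-size combinations and in 5 of 8 with suspicion for HCC added. With 8.1.3 read as a sufficient condition only, it is silent on those same cases. Both counts assume that *abnormal* and *elevated* AFP mean the same and that *and/or* is inclusive.

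The supportable consequence is limited. After a single finding, biopsy, histology and clonal-origin sequencing may be obtained at one site and omitted at another.

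Two larger inferences are tempting, and the documents do not support them.

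- A reader might infer that tumours would go undetected or that the SMC trigger would fail. AFP and liver MRI are scheduled for all subjects whatever the biopsy rule, Appendix 4 sends an abnormal AFP to evaluation and MRI, and the malignancy trigger in 11.5 and 12.3 does not mention biopsy.
- A reader might infer that, with at most 32 subjects, one mishandled case would change the trial's carcinogenicity conclusion. The plan defines no carcinogenicity endpoint, rate or threshold. Its summaries are descriptive, and SAP 7.9 gives AFP only descriptive statistics and a listing.

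No planned analysis fails because of this. It is a safety instruction that needs a single reading.

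**What to change.** Reconcile Protocol 8.1.3, 9.28 and Appendix 4 so that one identical trigger appears in all three. In the same edit:

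- use one AFP term throughout, either *abnormal* or *elevated*;
- state how the clinical evaluation and MRI step in Appendix 4 relates to biopsy;
- align the group described in the sequencing paragraph of Appendix 4 with the reconciled trigger.

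Which rule applies is the sponsor's clinical decision, and this review takes no position on it. The cost is minor wording in a protocol amendment. The scheduled AFP, MRI and biopsy visits and the sample size stay as they are.
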